6.3. Other endpoints

6.3.1. Healthcare Resources and Costs

The use of healthcare resources and costs in patients with RA treated with Tofacitinib in Greece will be examined using the following:

- The number of visits to a rheumatologist or other RA specialist since the last visit.
- The number of patients with diagnostic tests and the number of diagnostic tests since the last visit. Diagnostic tests include: WBC, ESR/CRP, glucose, hepatic enzymes, Urea, Creatinine, lipid profile, X-rays, other (summarised by visit).
- Hospitalisations since the last visit:
The number of patients who are hospitalised, the number of hospitalisations per patient and the number of days hospitalised per patient, the reason, overall and by type of hospitalisation (day care or overnight stay) will be derived.(summarised by visit).

In addition an economic evaluation will also be performed. This is not covered in this SAP.

6.4. Covariates

The following potential risk factors will be included as covariates in the logistic regression analyses of remission and LDA:

- Age:
Age at baseline will be included as a continuous covariate.
- Gender (male/female).
- Weight:
The weight (kg) at baseline will be included as a continuous covariate.
- Smoking history:
Smoking history will be included as a categorical covariate with five levels:
 - Never;
 - History but cessation of more than 3 years;
 - History but cessation of less than 3 years; Smoker, regular (≥ 1 cigarette/day); Smoker, low (< 1 cigarette/day).

If there are issues with the convergence of the model using the above categories, these will be collapsed into the following 3 categories:

- Never;
- Ex-Smoker; Smoker.

PFIZER CONFIDENTIAL

- Duration of Disease at Baseline:
Time (years) from RA diagnosis to inclusion in the study will be included as a continuous covariate.
- Serology at Baseline:
• Rheumatoid Factor (RF) will be included with two levels: positive and negative.
• Anti-citrullinated protein antibodies (ACPA) will be included with two levels: positive and negative.
- Previous DMARD use (number):
The number of previous biological (bDMARDs) will be included as a continuous covariate. See Appendix A1.2 for details of drugs to be considered as bDMARDs.
- Current concomitant treatment:
Two covariates will be fitted, one for the most common concomitant treatment (Yes/No) and one for the second most common concomitant treatment (Yes/No).
- Glucocorticoid dose:
The Glucocorticoid dose at baseline will be included as a continuous covariate.
- csDMARDs:
• The number of current conventional synthetic DMARDs (csDMARDs) at baseline will be included as a continuous covariate. See Appendix A1.2 for details of drugs to be considered as csDMARDs.
- The dose of csDMARDs at baseline will be included as a continuous covariate.
- Acute phase reactants:
ESR and CRP at baseline will be included as continuous covariates.
- DAS28-4 (CRP) score:
• DAS28-4 (CRP) at baseline will be included as a continuous covariate. This will be calculated as outlined in [Section 6.1.1](#).
- HAQ-DI score:
The HAQ-DI score at baseline will be included as a continuous covariate. This will be calculated as outlined in [Section 6.1.2.3](#).
- CDAI:
CDAI at baseline will be included as a continuous covariate. This will be calculated as outlined in [Section 6.1.2.4](#).
- Lipids:

PFIZER CONFIDENTIAL

The change from baseline at month 3 in Low-density lipoprotein (LDL) will be included as a continuous covariate.

- Hb levels:

The change from baseline at month 3 in hemoglobin (Hb) will be included as a continuous covariate.

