9.3. Variables

Variable	Role	Data source(s)	Operational definition
RA-treatment with Tofacitinib and/or other DMARDs – date of initiation	Exposure, Potential confounder, subgroup identifier	Case records and electronic Case Report Form (eDCT)	Details will be provided in Statistical Analysis Plan
RA treatment with Tofacitinib and/or other DMARDs – dose	Exposure, Potential confounder, subgroup identifier	Case records and eDCT	Details will be provided in Statistical Analysis Plan
RA treatment with Tofacitinib and/or other DMARDs - tolerability	Potential confounder, subgroup identifier	Case records and eDCT	Details will be provided in Statistical Analysis Plan
RA treatment with Tofacitinib and/or other DMARDs – route of administration	Potential confounder, subgroup identifier	Case records and eDCT	Details will be provided in Statistical Analysis Plan
Time of tofacitinib initiation	Exposure	Case records/eDCT	Details will be provided in Statistical Analysis Plan

Tofacitinib citrate
A3921342 NON-INTERVENTIONAL STUDY PROTOCOL
Version 2.0, 14 January 2020

Variable	Role	Data source(s)	Operational definition
Age	Baseline characteristic, potential confounder, sub-group identifier	Case records/eDCT	Details will be provided in Statistical Analysis Plan
Gender	Baseline characteristic, potential confounder, sub-group identifier	Case records/eDCT	Details will be provided in Statistical Analysis Plan
Height	Baseline characteristic, potential confounder, sub-group identifier	Case records/eDCT	Details will be provided in Statistical Analysis Plan
Weight	Baseline characteristic, potential confounder, sub-group identifier	Case records/eDCT	Details will be provided in Statistical Analysis Plan
Date of first diagnosis of RA	Baseline characteristic, potential confounder, sub-group identifier	Case records/eDCT	Details will be provided in Statistical Analysis Plan
Anti-citrullinated protein antibodies (ACPA)	Baseline characteristic, potential confounder, sub-group identifier	Case records/eDCT	Details will be provided in Statistical Analysis Plan
RF	Baseline characteristic, potential confounder, sub-group identifier	Case records/eDCT	Details will be provided in Statistical Analysis Plan
Structural damage	Baseline characteristic, potential confounder, sub-group identifier	Case records/eDCT	Details will be provided in Statistical Analysis Plan

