9.4.13. Treatment of Rheumatoid Arthritis (RA-Treatment) with Tofacitinib and/or Other DMARDs

At each visit dose and route of administration (if applicable) of treatment with Tofacitinib and/or other DMARDs will be documented. In addition, stop date of previous DMARD(s), start date of new DMARD(s) and reason for switch (lack of efficacy or intolerance) will be documented.

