9.7.3. Efficacy Analysis

9.7.3.1. Primary Analysis

The primary analysis will investigate the potential role of several baseline clinical and biochemical parameters as independent predictive factors of remission or LDA at month 6 of treatment, assessed by DAS28-4 (CRP) <2.6 and DAS28-4 (CRP) <3.2, respectively and will be calculated as follows:

$$\begin{aligned} \text{DAS28-4 (CRP)} = & 0.56 * \sqrt{(\text{TJC28})} + 0.28 * \sqrt{(\text{SJC28})} + 0.36 * \ln(\text{CRP in mg/l} + 1) \\ & + 0.014 * \text{PtGA in mm} + 0.96. \end{aligned}$$

This will be investigated using logistic regression. The potential predictive factors that may be considered include:

- Age;
- Gender;
- Weight;
- Smoking history;
- Time (years) from RA diagnosis;
- Serology: RF, ACPA;
- Previous biologic DMARD use (number);
- Current concomitant treatment;
- Glucocorticoid dose;
- csDMARDs: number and dose;
- Acute phase reactants: ESR and CRP;
- DAS28-4 (CRP) score;
- HAQ-DI score;
- CDAI;
- Lipids (LDL);
- Hb levels.

The effect of each factor will firstly be tested with a univariate logistic regression model. All potential factors with a p-value resulting from univariate analysis less than 10% will then be included in a multivariate model, along with any factors considered important from a clinical point of view. Predictive factors and their interactions will be chosen using a backward (step-down) selection. Predictive factors chosen will be those which have a p-value less than 5%. In the case of a significant interaction, all individual components of the interaction will be “forced” in the model, whether they are statistically significant or not. It is anticipated that the primary model will include approximately ten covariates.

Full details, including methods for handling missing data, will be provided in the SAP. For the primary endpoints of remission or LDA, a non-responder imputation will be used for patients who have missing data at month 6.

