11. APPENDICES

11.1. APPENDIX 1: DATA DERIVATION DETAILS

A1.1 Definition and use of visit windows in reporting

Visit windows will be used for efficacy variables, and for any safety displays that display by month.

Visit Label	Target Day	Definition [Day window]
Enrolment	1	Day 1 or before
Month 3	91	Day 2 to 137
Month 6	183	Day 138 to Day 274
Month 12	365	Day 275 onwards

If two or more visits fall into the same window, keep the one closest to the Target Day. If two visits are equal distance from the Target Day in absolute value, the later visit should be used.

(Safety analysis may follow Pfizer standard).

A1.2 Definitions of bDMARDs and csDMARDs

The following drug names will be used to determine whether drugs are bDMARDs or csDMARDs

List of bDMARD (Brand name should be used to be able to track biosimilars)

[figure not shown]
Humira (Adalimumab)

Cimzia (Certolizumab Pegol)
Enbrel (Etanercept)
Simponi (Golimumab)
Remicade (Infliximab)
Orencia (Abatacept)
Roactemra (Tocilizumab)
Kineret (Anakinra)
Mabthera (Rituximab)
Benepali (Etanercept)
Inflectra (Infliximab)
Other

List of csDMARD

Methotrexate
Leflunomide
Hydroxychloroquine sulfate
Sulfasalazine
Other

CCI

PFIZER CONFIDENTIAL

Final Version 1.0

28-Jan-2020

Page 36 of 36

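### csDMARD dose is one continuous covariate across several drugs, with no common scale and no coding for combinations or non-users, so its coefficient cannot be read as a dose effect

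*SAP*

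**What the plan says.** Protocol Section 9.7.3.1 lists "csDMARDs: number and dose" among the candidate predictors of remission or LDA. Section 9.3 has a row for "RA treatment with Tofacitinib and/or other DMARDs – dose" and leaves its operational definition to the SAP.

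SAP Section 6.4 turns the candidate into two terms. One is a count: "The number of current conventional synthetic DMARDs (csDMARDs) at baseline will be included as a continuous covariate". The other is the dose: "The dose of csDMARDs at baseline will be included as a continuous covariate".

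Appendix A1.2 decides what is a csDMARD by name: "The following drug names will be used to determine whether drugs are bDMARDs or csDMARDs". The csDMARD list holds methotrexate, leflunomide, "Hydroxychloroquine sulfate", sulfasalazine and an open category.

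The dose data are planned. Protocol Section 9.4.13 states: "At each visit dose and route of administration (if applicable) of treatment with Tofacitinib and/or other DMARDs will be documented".

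The only other terms in Section 6.4 that could identify a csDMARD are two Yes/No indicators for the most common and second most common concomitant treatment. They are not stated to be csDMARDs.

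**The concern.** A continuous covariate needs one scale on which a unit step means the same for every patient. Here a single number has to serve at least four drugs, and neither document says how it is built. Three derivations are open: how doses of different drugs are made comparable, what a patient on two csDMARDs receives, and what a patient on none receives. The last two will arise. The SAP counts csDMARDs per patient, and its treatment label in Section 2.3 covers tofacitinib both alone and in combination.

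Identifying predictors is the primary objective. The dose term is a candidate in all four logistic models (remission and LDA, months 6 and 12). Under SAP Section 8.1.1 it is screened alone at p < 0.10 and, if it enters the multivariate model, kept at p < 0.05. Two errors are possible: a drug difference may be reported as a dose effect, or a real dose effect may be diluted and dropped.

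**Working it through.** **The plan's own figure.** Protocol Section 9.5 uses N = 10k/p. With k = 10 and p = 0.50, N = 10 × 10 / 0.50 = 200 patients and 100 events, as stated. This does not test how a covariate is coded, but it sets the parameter budget for the fix.

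**Share of variance that lies between drugs.** Take users of two drugs, one drug per patient. Assumptions, none of them in the documents: R is the ratio of the mean numerical doses, q is the share of users on the drug with the larger numbers, and the within-drug coefficient of variation (CV) is 0.3. With the smaller mean set to 1:

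- between-drug variance b = q(1 − q)(R − 1)²
- within-drug variance w = CV²[(1 − q) + qR²]
- share = b/(b + w)

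For R = 2 and q = 0.05: b = 0.05 × 0.95 × 1 = 0.0475; w = 0.09 × (0.95 + 0.20) = 0.1035; share = 0.0475/0.1510 = 31%. For R = 5 and q = 0.50: b = 0.25 × 16 = 4; w = 0.09 × 13 = 1.17; share = 4/5.17 = 77%.

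| R | q = 5% | 10% | 20% | 30% | 50% |
|---|---|---|---|---|---|
| 1 | 0% | 0% | 0% | 0% | 0% |
| 2 | 31% | 43% | 53% | 55% | 53% |
| 5 | 79% | 82% | 83% | 82% | 77% |
| 10 | 88% | 88% | 87% | 86% | 82% |
| 20 | 90% | 90% | 89% | 87% | 83% |

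**Non-users.** Suppose 40% of patients take no csDMARD and are coded 0 (both assumed). With one drug only, the between-group variance is 0.6 × 0.4 × 1² = 0.24 and the within-user variance is 0.6 × 0.09 = 0.054. So 0.24/0.294 = 82% of the variance is use versus non-use. With two drugs, use and drug together reach up to 91%. If non-users are left missing instead, SAP Section 7 has no rule for missing covariates.

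**Effect on selection.** Logistic simulation with n = 200, response near 50%, every patient on one of the two drugs, q from 10% to 50%, and 500 replicates per setting (standard error of a pass rate at most √(0.25/500) = 2.2 percentage points):

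- *No dose effect, between-drug log odds ratio 0.8.* Pooled dose passes the p < 0.10 screen in about 10% of replicates at R = 1, 28–66% at R = 2 and 42–83% at R = 10 to 20.
- *True dose effect of 0.5 log-odds per within-drug SD, no drug effect.* The pass rate is about 96% at R = 1, 69–75% at R = 2 and 14–28% at R = 10 to 20.
- *Dose effect +0.5, drug effect −0.8.* The pooled coefficient turns negative at R = 10 to 20 (−0.12 to −0.23 per SD).
- *Dose standardised within drug plus a drug indicator.* Dose passes in about 6–12% of replicates with no dose effect and 93–98% with the true effect, whatever R is.

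**The case against.** The strongest reply is that this is an undefined derivation rather than a chosen error. The SAP does not say that raw doses are added together, and a programmer might standardise them. That is fair, but one continuous term is what the text specifies, and the protocol had passed the definition to this document. A redacted block follows the csDMARD list. Nothing visible refers to a dose conversion there.

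Second, the two concomitant-treatment indicators could take up part of the drug effect. If they happen to be the relevant csDMARDs, this stands for the multivariate step: with a drug indicator in the model, false retention at p < 0.05 is about 2–6%. It does not protect the univariate screen, where dose stands alone. Nor does it restore power for a true dose effect of 0.5 per SD with no drug effect: 28–74% at R = 10 to 20, against 89–94% with standardised dose. Some of the drug-adjusted fits gave convergence warnings, so these figures are approximate.

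Third, dose is one candidate among many, the protocol lists factors that may be considered, and SAP Section 4 sets no formal hypotheses. This limits the reach of the point. A reader might infer that the primary analysis as a whole is invalid. The documents do not support that: the term may be dropped in selection, and the harm falls on whether this one factor is selected and how its coefficient is read.

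A reader might also infer that the coefficient measures which drug was used and not dose. The documents do not support this either, because they give neither drug mix nor dose scales. It is a fair description of users at R of about 5 or more and about half true at R = 2. It is untrue at R = 1 or if nearly all users take one drug, and it leaves out use versus non-use.

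**Conclusion.** The point holds in this form: as specified, the csDMARD dose coefficient mixes use, drug identity and dose, and cannot be read as a dose effect. That conclusion needs no assumed scale. It follows from the missing unit, the missing combination rule and the missing value for non-users. Two programmers could build different covariates from the same text.

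The size does rest on assumptions: two drugs, one per patient, within-drug CV 0.3, q from 5% to 50%. The between-drug share among users then runs from 0% (R = 1) through 31–55% (R = 2) to 77–90% (R = 5 to 20). The simulated pass rates add an assumed drug or dose effect and should be read as orders of magnitude. The sample size figure is unaffected. The definition should be corrected before analysis because it feeds a candidate for the primary models, but it does not threaten the study as a whole.

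**What to change.** In SAP Section 6.4, replace the pooled dose term with one of the following, chosen before analysis:

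- **(a)** Yes/No indicators for the main csDMARDs. If the indicators cover every csDMARD in use, the csDMARD count equals their sum, so they should replace the count rather than sit beside it.
- **(b)** Dose standardised within drug, or the dose of one named drug only, set to 0 for non-users and accompanied by an indicator of use, with a stated rule for patients on more than one csDMARD.

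In either case, say how the new terms relate to the two concomitant-treatment indicators, so that the same drug is not entered twice.

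The cost is SAP wording, using dose data the protocol already plans to record at each visit. The downside is possibly one or more extra candidate parameters. Option (b) turns one term into at least two. Option (a) with two indicators in place of dose and count adds none, and each further indicator adds one. By the plan's own rule an eleventh covariate would need 10 × 11 / 0.50 = 220 patients, or would leave 100/11 = 9.1 events per variable at 200. Extra terms should therefore be counted against the ten.

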NON-INTERVENTIONAL (NI) STUDY PROTOCOL

This document contains confidential information belonging to Pfizer. Except as otherwise agreed to in writing, by accepting or reviewing this document, you agree to hold this information in confidence and not copy or disclose it to others (except where required by applicable law) or use it for unauthorized purposes. In the event of any actual or suspected breach of this obligation, Pfizer must be promptly notified.

Study Information

Title	BASELINE VARIABLES PREDICTING TREATMENT RESPONSE AT 6 MONTHS IN ADULT RHEUMATOID ARTHRITIS PATIENTS TREATED WITH TOFACITINIB 5MG BID IN A NON-INTERVENTIONAL SETTING (TREAT-RA)
Protocol number	A3921342
Protocol version identifier	2.0
Date	14 January 2020
Active substance	L04AA29 tofacitinib
Medicinal product	Xeljanz
Research question and objectives	The primary objective of this non-interventional study is to identify baseline characteristics of patients that predict response at 6 months of treatment. The study also aims to describe the treatment patterns of RA patients prescribed tofacitinib in a real-world setting and assess the effect of treatment on patient quality of life and physical function. Finally the study will assess the use of healthcare resources and costs in patients with RA treated with tofacitinib in Greece.
Author	PPD [REDACTED] MD, MSc PPD [REDACTED] PPD [REDACTED] [REDACTED]

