8.1. Endpoints

8.1.1. Primary Endpoint:

- a. Identify baseline characteristics that predict remission or LDA at month 6 of treatment, assessed by DAS28-4 (CRP) <2.6 and DAS28-4 (CRP) <3.2, respectively.

8.1.2. Key Secondary Endpoints:

- a. Identify baseline characteristics that predict remission or LDA at month 12 of treatment, assessed by DAS28-4 (CRP) <2.6 and DAS28-4 (CRP) <3.2 , respectively.
- b. Change from Baseline in DAS 28-4 (ESR) and DAS 28-4 (CRP) at any time point.
- c. Change from Baseline in HAQ-DI at any time point.
- d. Rate of remission at any other time point, as assessed by: SDAI ≤3.3 ; CDAI ≤2.8 ; DAS 28-4 (ESR) <2.6 and DAS28-4 (CRP) <2.6 .
- e. Rate of LDA at any other time point, as assessed by: SDAI ≤11 ; CDAI ≤10 ; DAS 28-4 (ESR) <3.2 and DAS28-4 (CRP) <3.2 .
- f. Percentage HAQ-DI responders (decrease of at least 0.22) at any time point.
- g. Change from Baseline in EuroQol EQ-5D Health State Profile at any time point.
- h. Change from Baseline in FACIT-Fatigue scale at any time point.
- i. Change from baseline in duration of morning stiffness at any time point.
- j. Change from Baseline in Work Productivity and Activity Impairment (WPAI) Questionnaire at any time point.
- k. Assess the use of healthcare resources and costs in patients with RA treated with tofacitinib in Greece.
- l. Patients satisfaction with treatment at baseline and month 12.
- m. Describe the treatment patterns of RA patients prescribed tofacitinib in a real-world setting.

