1. AMENDMENTS FROM PREVIOUS VERSION(S)

This is the first version of the statistical analysis plan (SAP). There are no changes to the analyses specified in the protocol.

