6. ENDPOINTS AND COVARIATES

6.1. Efficacy/Effectiveness Endpoint(s)

Baseline measurements for all endpoints are the last measurement before Tofacitinib treatment, up to 28 days before starting Tofacitinib. Change from baseline at a timepoint will be calculated as:

$$\text{Measurement at visit} - \text{Measurement at baseline}$$

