7.1.4. WPAI

A domain score can only be calculated if none of the required items have missing data. If any of the required items have missing data the domain score will be set to missing. Missing data will not be imputed.

8. STATISTICAL METHODOLOGY AND STATISTICAL ANALYSES**8.1. Statistical methods****8.1.1. Logistic Regression Analysis**

The potential role of several baseline clinical and biochemical parameters as independent predictive factors of remission or LDA will be investigated using logistic regression. The potential predictive factors to be considered are described in [Section 6.4](#).

The effect of each factor will firstly be tested with a univariate logistic regression model. All potential factors with a p-value resulting from univariate analysis less than 10% will then be included in a multivariate model, along with any factors considered important from a clinical point of view. Predictive factors and their interactions will be chosen using a backward (step-down) selection. Predictive factors chosen will be those which have a p-value less than 5%. In the case of a significant interaction, all individual components of the interaction will be “forced” in the model, whether they are statistically significant or not.

The SAS procedure PROC LOGISTIC will be used to perform the logistic regression analyses.

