8.2.5. Summary of Analyses

Outcome	Analysis Set	Supports Protocol Objective Number	Subgroups	Statistical Method	Covariates/ Strata	Missing Data
Rate of Remission at Month 6	FAS	1	None	Logistic regression	Potential predictive factors outlined in Section 6.4	NRI
Rate of LDA at Month 6	FAS	1	None	Logistic regression	Potential predictive factors outlined in Section 6.4	NRI
Rate of Remission at Month 12	FAS	2	None	Logistic regression	Potential predictive factors outlined in Section 6.4	NRI
Rate of LDA at Month 12	FAS	2	None	Logistic regression	Potential predictive factors outlined in Section 6.4	NRI
EQ-5D	FAS	2	None	MMRM	Baseline score, timepoint fitted as a fixed effect and baseline by timepint interaction	MMRM
FACIT-Fatigue	FAS	2	None	MMRM	Baseline score, timepoint fitted as a fixed effect and baseline by timepint interaction	MMRM
WPAI	FAS	2	None	MMRM	Baseline score, timepoint fitted as a fixed effect and baseline by timepint interaction	MMRM

PFIZER CONFIDENTIAL

Final Version 1.0

28-Jan-2020

Page 33 of 36

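### SAP 6.4 defines the LDL and Hb covariates as change at month 3, which puts two on-treatment terms into a model of baseline predictors and leaves baseline LDL and Hb off the candidate list.

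*SAP*

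**What the plan says.** The protocol points to baseline throughout. Its title reads "BASELINE VARIABLES PREDICTING TREATMENT RESPONSE AT 6 MONTHS". The primary endpoint in section 8.1.1 is to "Identify baseline characteristics that predict remission or LDA at month 6 of treatment". Section 9.7.3.1 describes the primary analysis as one of baseline parameters and lists LDL and Hb levels among the factors that may be considered, with no mention of change or of month 3.

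SAP 8.1.1 keeps the baseline description: "The potential role of several baseline clinical and biochemical parameters as independent predictive factors of remission or LDA will be investigated using logistic regression". It takes its candidates from SAP 6.4, where the last two entries read:

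- LDL: "The change from baseline at month 3 in Low-density lipoprotein (LDL) will be included as a continuous covariate".
- Hb: "The change from baseline at month 3 in hemoglobin (Hb) will be included as a continuous covariate".

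The summary table in SAP 8.2.5 gives the covariates of all four logistic models as "Potential predictive factors outlined in Section 6.4". SAP section 1 says "There are no changes to the analyses specified in the protocol".

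**The concern.** A month-3 value is not known when tofacitinib is started, so it cannot help predict at that point who will respond. This holds whether the definition was deliberate or a slip. Four consequences follow.

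- **Mislabelled predictor.** A change in LDL or Hb by month 3 may only reflect early response. If selected, it would be reported from a model described as one of baseline parameters.
- **Lost candidate.** A real effect of baseline LDL or Hb can be missed. It can also show up only through a change term with the opposite sign, because a change score tends to correlate negatively with its own baseline.
- **Effect on other factors.** Once in the multivariable model, a change term can shift the coefficients of genuine baseline factors. Size and direction depend on correlations that the documents do not give.
- **Lost patients.** SAP section 7 has no rule for missing covariates. Under complete-case fitting, a patient without the change value leaves any model containing the term, even if non-responder imputation has supplied the outcome.

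**Working it through.** **Text comparison**

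| Place | Timing of predictors |
|---|---|
| Protocol title, 8.1.1, 9.7.3.1 | Baseline |
| SAP 8.1.1 | Baseline; candidates taken from 6.4 |
| SAP 6.4: weight, glucocorticoid dose, csDMARD number and dose, ESR, CRP, DAS28-4 (CRP), HAQ-DI, CDAI | Explicitly at baseline |
| SAP 6.4: LDL, Hb | Change at month 3 |
| SAP Appendix A1.1, month-3 window | Day 2 to Day 137 |

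Under that window the second value in the change is always post-baseline. LDL and Hb are the only two covariates explicitly defined by a post-baseline value; concomitant treatment is called current, with no time point.

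**The plan's study size.** Protocol 9.5 uses N = 10k/p with k = 10 covariates and p = 0.50. This gives 10 × 10 / 0.50 = 200 patients and 100 events, which reproduces the stated figure. Swapping one continuous term for another changes neither k nor N.

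**Illustrations.** N = 200 and 50% response follow Protocol 9.5. All effect sizes, correlations and missing-data rates are assumptions. Parts (a) and (b) use 3,000 simulated samples per setting and univariate Wald tests. Part (c) uses 400,000 subjects per setting.

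(a) *Lost candidate.* Response depends on baseline Hb only (log-OR 0.4 to 0.5 per SD), and the month-3 value adds nothing. With visit-to-visit correlation ρ and equal SDs, corr(baseline, change) = −√((1 − ρ)/2).

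| ρ | corr(baseline, change) | Change passes 10% screen |
|---|---|---|
| 0.9 | −0.22 | 16% to 19% |
| 0.7 | −0.39 | 29% to 37% |
| 0.5 | −0.50 | 38% to 52% |

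Baseline Hb itself passes in 87% to 96%.

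(b) *Early-response marker.* The change correlates 0.1 to 0.4 with early response, and early response has log-OR 0.6 to 1.2. The change passes the 10% screen in 12% to 85% of samples and reaches p < 0.05 in 6% to 76%.

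(c) *Another baseline factor* with direct log-OR 0.3, once a change with log-OR 0.3 or 0.6 is in the model.

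| Correlation of factor with change | Effect on the factor |
|---|---|
| +0.2 to +0.7 | log-OR falls 15% to 57% |
| 0 | log-OR moves +2% to +8% |
| −0.2 | OR rises from 1.26 to 1.34, or from 1.18 to 1.35 |
| −0.5 | OR rises from 1.16 to 1.35, or from 1.01 to 1.36 |

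(d) *Complete-case loss.* If 10% lack one change value, 200 × 0.9 = 180 patients remain. That is 90 events, or 90/10 = 9.0 per variable with ten covariates, against the planned 10. If both terms enter with independent 10% missingness, 200 × 0.9 × 0.9 = 162 remain, giving 81 events and 8.1 per variable.

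**The case against.** The strongest reply is that the choice may be deliberate and within the SAP's remit. Protocol 9.7.3.1 offers LDL and Hb only as factors that may be considered and gives no time point on either line. The objectives (Protocol section 8, SAP 2.4) speak of predictive factors without the word baseline. The protocol's background cites early disease control as a determinant of later effect. Protocol 9.7 lets the SAP modify the plan. This makes intent plausible but does not remove the conflict. SAP 8.1.1 defines the model as one of baseline parameters, Protocol 9.7 requires an amendment for major changes to the primary analysis, and SAP section 1 declares no change.

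Baseline LDL or Hb could also enter through the clause that admits clinically important factors to the multivariable model. That is true, but the clause names neither. They are therefore not prespecified, rather than strictly barred.

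The reach is limited in one respect: the univariate results for all other candidates are untouched, and their adjusted coefficients change only if a change term enters the multivariable model.

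Several points about the illustrations stand.

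- The low end of (b) is close to the nominal 10%, so that range runs from almost no effect to a large one.
- The sign reversal in (a) depends on the assumption that month-3 Hb adds nothing. If the change is instead unrelated to both baseline and response, it passes at about the nominal rate (9% in a 1,000-sample run at OR 1.6 per SD), against 94% for baseline Hb. The candidate is still lost.
- Part (c) is what adjustment for any correlated covariate does. It does not isolate harm from timing.
- In (d), patients without a baseline value are lost under either definition, so the avoidable loss is smaller than shown. Blood tests are grouped by visit, so 180 is nearer than 162.

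**Conclusion.** The concern holds. Followed exactly, the SAP puts two on-treatment terms among the candidates for all four predictor models and does not prespecify baseline LDL or Hb. This contradicts the primary endpoint, the protocol's primary analysis and the SAP's own description of the model, and it makes the statement in SAP section 1 inaccurate. That conclusion rests on the text alone.

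The size rests on assumed effects and correlations. If baseline Hb matters, the chance of detecting it at the screen falls from about 9 in 10 to between roughly 1 in 6 and 1 in 2. If the change only marks early response, the chance that it enters the multivariable model runs from near nominal to 85%. The events-per-variable loss is secondary and depends on an assumed missing-data rate. Because the defect bears on the primary question and is cheap to remove, it should be corrected before analysis.

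**What to change.** In SAP 6.4, replace the two entries with LDL at baseline and Hb at baseline, each as a continuous covariate, for the month-6 and month-12 models. State that the rule in SAP 6.1, "Baseline measurements for all endpoints are the last measurement before Tofacitinib treatment, up to 28 days before starting Tofacitinib", applies to these covariates too, since as written it covers endpoints.

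If month-3 changes are of interest, put them in a separate month-3 landmark analysis, labelled as on-treatment and kept outside the primary model. Declare it in SAP section 1 as an addition to the protocol.

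The cost is two lines of SAP text, plus one line in section 1 if the landmark analysis is kept. The study size stays at 200. Protocol 9.4.2.1 documents blood biochemistry and haematology at baseline but does not name LDL or Hb. The schedule of activities has no row for these tests, and Protocol 9.7.2 keeps laboratory data used for eligibility out of the database unless otherwise noted. These sections should be reconciled to confirm that the baseline values are captured. The change score needs the baseline value as well, so the baseline definition cannot lose more patients.
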